6.7.3 Immune effector cell-associated neurotoxicity syndrome (ICANS)

Immune effector cell-associated neurotoxicity syndrome (ICANS) may have features that overlap with other encephalopathies but has the more specific characteristic of an awake subject who is mute and does not respond verbally or physically to an examiner. In a small number of subjects, mild CNS toxicity occurs in the absence of CRS. The great majority of subjects, CNS toxicity appears concurrent or shortly after CRS, and assessments and management of these subjects according to CRS guidelines above is indicated. If neurologic symptoms develop, assessment and grading for ICANS be completed at least every 12 hours including the 10-point ICE score assessment (Section 13.5). Subjects with Grade 2 ICANS should have neuroimaging studies to assess CNS edema. Neurotoxicity may require transfer to the ICU for close monitoring or intubation for airway protection even in the absence of severe CRS. Adverse events of CRS are graded according to the ASTCT consensus grading scale (Section 13.5).

- **Symptoms that occur in the absence of advanced ICANS (where advanced ICANS is defined as Grade 3 ICANS or Grade 2 ICANS without CRS)**, such as headache, tremor, myoclonus, asterixis, hallucinations, weakness, or imbalance may be managed symptomatically.
- **Subjects with advanced ICANS (Grade 2 ICANS and no CRS, or subjects with Grade 3 ICANS)** should be treated with corticosteroids (methylprednisolone 2 mg/kg x1 followed by 0.5 mg/kg q6h; or dexamethasone 0.4 mg/kg x1 followed by 0.1 mg/kg q6h; or equivalent). Steroids should be tapered to off within 1 week.
- **Advanced ICANS symptoms that are persistent 24 hours after steroid administration** may require anti-T cell therapy such as such as alemtuzumab (12 mg IV over 4 hours QD x5d), high dose cyclophosphamide, or ATG (2 mg/kg/day IV).

Grade 4 ICANS should be reported immediately to the medical monitor. If the event does not resolve to Grade 1 ICANS within 72 hours, a criterion for pausing study enrollment is reached.

6.7.4 Tumor Lysis Syndrome

Tumor lysis syndrome (TLS) after cell therapy is uncommon even in high-risk situations. However, precautions such as intravenous hydration and prophylactic allopurinol or febuxostat should be administered prior to the initiation of conditioning lymphodepleting chemotherapy in those subjects with elevated uric acid or high tumor burden.

TLS prophylaxis may be used per institutional standard. Following therapy, TLS diagnosed solely based on laboratory criteria should be managed initially per institutional standard with therapy directed at uric acidemia such as allopurinol or febuxostat. For persistent symptoms, subjects should receive intravenous hydration and additional uric acid therapy such as rasburicase. All subjects with clinical TLS should be admitted for in-hospital treatment and monitoring.

6.7.5 Uncontrolled T-cell Proliferation

NTLA-5001 cells could theoretically proliferate without control of normal homeostatic mechanisms. This risk is reduced by the use of targeted gene insertion using AAV [REDACTED]

[REDACTED] Other viral insertion methods, such as the use of lentivirus, cause transgene insertion at random sites, which is thought to pose a higher risk to the interruption of normal cellular functions. Lymphocytes will be monitored by hematology laboratory assessments at each visit. A lymphocyte spike is typically seen around the time of peak cell expansion after adoptive therapy, and this finding alone should not be a reason to intervene. If the WBC count rises above normal values and is sustained 14 days after infusion, the subject should be assessed for clonal T cell proliferation, including assessment of rapidly progressing AML. At each visit, history and physical should include assessment for enlarged lymph nodes or immune dysfunction. Any sustained elevation of WBC due to lymphocytosis at any time should be treated as presumed NTLA-5001 proliferation while evaluation continues, and a peripheral blood sample should be sent for evaluation of cell kinetics to assess for proliferating NTLA-5001 cells.

If uncontrolled proliferation of NTLA-5001 cells occurs, subjects may be treated with corticosteroids (methylprednisolone 2 mg/kg x1 followed by 0.5 mg/kg q6h; or dexamethasone 0.4 mg/kg x1 followed by 0.1 mg/kg q6h; or equivalent). If symptoms persist, or recur as steroids are tapered, subjects may require anti-T cell therapy such as such as alemtuzumab (12 mg IV over 4 hours QD x5d), high dose cyclophosphamide, or ATG (2 mg/kg/day IV).

6.7.6 Autologous GvHD

After autologous HCT or autologous CAR-T therapy, a GvHD-like syndrome which is clinically and histologically indistinguishable from allogeneic GvHD has been described in the skin, liver and gastrointestinal tract. Autologous GvHD is an autoimmune syndrome initiated by auto-reactive T cells that recognize self-major histocompatibility complex (MHC) class II antigens. The diagnosis of autologous GvHD can be made with clinical suspicion, inspection and biopsy of affected sites, and exclusion of other possible cases of symptoms such as infections, drug effect and engraftment syndrome.

If autologous GvHD occurs, subjects may be treated with corticosteroids (methylprednisolone 2 mg/kg x1 followed by 0.5 mg/kg q6h; or dexamethasone 0.4 mg/kg x1 followed by 0.1 mg/kg q6h; or equivalent). If symptoms persist, or recur as steroids are tapered, subjects may require sitagliptin (100–200 mg/day orally [PO]), ruxolitinib (10 mg PO twice daily [BID]), or anti-T cell therapy such as such as alemtuzumab (12 mg IV over 4 hours QD x5d).

6.7.7 Hemophagocytic Lymphohistiocytosis

After ATC, symptoms of CRS may subsequently evolve in some subjects to hemophagocytic lymphohistiocytosis (HLH)-like symptomatology. HLH related to adoptive therapy may be identified by a characteristic set of signs, including ferritin level of > 100,000 ng/mL with at least 2 of the following: Grade 3 or greater AST/ALT elevation or hyperbilirubinemia; Grade 3 or greater oliguria or increase in serum creatinine; Grade 3 or greater pulmonary edema; or hemophagocytosis in the bone marrow.

If HLH occurs, subjects may be treated with corticosteroids (methylprednisolone 2 mg/kg x1 followed by 0.5 mg/kg q6h; or dexamethasone 0.4 mg/kg x1 followed by 0.1 mg/kg q6h; or equivalent). If symptoms persist, or recur as steroids are tapered, subjects may receive tocilizumab (8 mg/kg IV) and/or anakinra (initially 2 mg/kg/day increasing by 1 mg/kg up to 8 mg/kg/day).

6.7.8 On-target/Off-tumor Toxicity

WT1 protein is expressed by a limited number of normal tissues, including CD34+ stem cells in the bone marrow, mesothelial linings of the peritoneum and pleura, testes/ovaries, fallopian tubes, and on podocytes of the kidney glomerulus. NTLA-5001 has the potential to cause inflammation or cell destruction at these sites through recognition of WT1 processed and presented on HLA class I, which is termed on-target/off-tumor toxicity. Monitoring for on-target/off-tumor toxicity includes physical examination observations, laboratory measures, and AE assessments at each visit to identify symptoms of tissue inflammation. History questions at each visit will interrogate reproductive history, testicular/scrotal pain, swelling, and erythema for males and lower abdominal pain or vaginal bleeding for women. Physical exam at each clinic visit should also assess for any new pleural or peritoneal effusions. It is recommended that positive history be followed up with work-up to assess the etiology as appropriate, including thoracic imaging, testicular US, abdominal US, pelvic exam, pregnancy test, thyroid and PRL levels, or endometrial biopsy as indicated. In addition, specific monitoring is included for signs at each of these organ sites (see Schedule of Activities). CD34+ bone marrow cells will be monitored at Week 4, 8, 16, and then at 12-week intervals for the duration of the study. Renal podocyte function will be assessed by urinalysis for proteinuria 1 week following NTLA-5001 then at each study visit.

- If signs, symptoms, and follow up evaluations suggest that bone marrow dysfunction, renal dysfunction, or mesothelial inflammation is potentially due to NTLA-5001, subjects should receive corticosteroids (methylprednisolone 2 mg/kg x1 followed by 0.5 mg/kg q6h; or dexamethasone 0.4 mg/kg x1 followed by 0.1 mg/kg q6h; or equivalent). During steroid taper, systematic assessment for recurrence of toxicity should be performed.

- If symptoms persist, or recur as steroids are tapered, subjects may require anti-T cell therapy such as such as alemtuzumab (12 mg IV over 4 hours QD x5d), high dose cyclophosphamide, or ATG (2 mg/kg/day IV).

7 DISCONTINUATION OF STUDY INTERVENTION AND SUBJECT DISCONTINUATION/WITHDRAWAL

7.1 Discontinuation of Study Treatment

In the event of an IRR, the infusion of study drug will be slowed or stopped. The following events in relation to an IRR will result in permanent discontinuation of study drug:

- The IRR is severe, and the decision is made by the investigator and/or Medical Monitor to not resume the infusion.
- The IRR is mild or moderate but does not resolve in a timeframe that allows completion of the infusion of study drug within the 4-hour window noted in Section 6.2.3.

Those subjects who receive a partial infusion will continue on study and will attend all study visits and have all tests performed per the SoA (Section 1.3). Subjects who receive a partial infusion in Part 1 will be replaced as explained in Section 4.1.1.

7.2 Discontinuation/Withdrawal from the Study

All subjects enrolled in the study will be followed for 112 weeks unless a subject:

- withdraws consent from study,
- dies, or
- is lost to follow-up.

If the subject withdraws consent for disclosure of future information, the Sponsor may retain and continue to use any data collected before such a withdrawal of consent.

If a subject withdraws from the study, he/she may request destruction of any samples taken and not tested, and the investigator must document this in the site study records.

The investigator should document all refusals and withdrawals and shall ensure that no data for the clinical trial are collected from subjects that refuse to participate in or have withdrawn from the clinical trial.

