6.2.1.2 Definition of a Dose-limiting Toxicity

DLTs are defined as events with onset within 28 days of infusion as follows:

- Any Grade 4 CRS per American Society for Transplantation and Cellular Therapy (ASTCT) consensus criteria, and Grade 3 CRS that does not resolve to Grade 2 within 72 hours
- Any Grade 3/4 neurotoxicity per ASTCT immune effector cell-associated neurotoxicity syndrome (ICANS) consensus grading criteria for adults
- Any Grade 4 acute GVHD of any duration; Grade 2 or 3 acute GVHD requiring systemic steroid treatment that does not resolve to \leq Grade 1 within 7 days.
- Acute infusion reaction: Reactions related to NTLA-5001 occurring within 2 hours of infusion that are not reversible to \leq Grade 2 within 24 hours.
- Grade 4 neutropenia or thrombocytopenia lasting more than 28 days that is not attributable to underlying disease or lymphodepletion chemotherapy
- Other severe organ toxicity that is not attributable to underlying disease or lymphodepletion chemotherapy as follows: Grade 4 toxicity that is a cardiac disorder, hepatobiliary disorder, renal disorder, respiratory disorder, or vascular disorder (per CTCAE); Grade 3 cardiac, respiratory, or vascular disorder that does not resolve to Grade 2 or lower within 72 hours; or Grade 3 hepatobiliary or renal disorder that does not resolve to Grade 2 or lower within 7 days.
- Grade 5 events without clinical or radiological evidence of disease progression which are related to NTLA 5001.

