7.3 Lost to Follow-up

A subject will be considered lost to follow-up if he or she repeatedly fails to return for scheduled visits and is unable to be contacted by the study site.

The following actions must be taken if a subject fails to return to the clinic for a required study visit:

- The site must attempt to contact the subject and reschedule the missed visit as soon as possible and counsel the subject on the importance of maintaining the assigned visit schedule and ascertain whether or not the subject wishes to and/or should continue in the study.
- Before a subject is deemed lost to follow up, the investigator or designee must make every effort to regain contact with the subject (where possible, 3 telephone calls and, if necessary, a

certified letter to the subject's last known mailing address or local equivalent methods). These contact attempts should be documented in the subject's medical record.

- Should the subject continue to be unreachable, he/she will be considered to have withdrawn from the study. For subjects who are lost to follow-up, the investigator can search publicly available records where permitted to ascertain survival status. This ensures that the data set(s) produced as an outcome of the study is/are as comprehensive as possible.

Discontinuation of specific sites or of the study as a whole are handled in Section [11.1.11](#).

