8.5.6 Follow-up of Adverse Events and Serious Adverse Events

All AEs occurring during or after the subject has discontinued the study are to be followed up until resolved or judged to be no longer clinically significant, or until they become chronic to the extent that they can be fully characterized in the opinion of the investigator. After 112 weeks, any continuing AEs will be followed under a separate long-term follow-up protocol.

If during AE follow-up, the AE progresses to an SAE, or if a subject experiences a new SAE, the investigator must immediately report the information to the Sponsor.

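### Protocol 7.2 stops data collection for every withdrawn subject and 7.3 counts lost subjects as withdrawn, which conflicts with the adverse event follow-up required by 8.5.6

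*Protocol*

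**What the plan says.** Protocol 7.2 gives three reasons for ending the 112-week follow-up: withdrawal of consent, death and loss to follow-up. Section 4.2 gives the same three. For a subject who refuses later disclosure of information, 7.2 keeps what is already in hand: "the Sponsor may retain and continue to use any data collected before such a withdrawal of consent". Its closing sentence makes the investigator ensure that "no data for the clinical trial are collected from subjects that refuse to participate in or have withdrawn". That sentence has no exception for vital status or open AEs.

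Protocol 7.3 sets out the contact attempts for missed visits and then says: "Should the subject continue to be unreachable, he/she will be considered to have withdrawn from the study". The same bullet continues: "For subjects who are lost to follow-up, the investigator can search publicly available records where permitted to ascertain survival status". Its stated aim is a data set that is as complete as possible.

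Protocol 8.5.6 says: "All AEs occurring during or after the subject has discontinued the study are to be followed up until resolved". The sentence goes on to allow follow-up to end when the event no longer matters clinically or has become chronic and well characterised. It does not exempt withdrawn subjects.

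**The concern.** Safety is the primary endpoint, and DLTs drive dose escalation. Several DLT criteria in 6.2.1.2 turn on how long an event lasts. One example is "Grade 3 hepatobiliary or renal disorder that does not resolve to Grade 2 or lower within 7 days"; others use 72 hours for Grade 3 cytokine release syndrome or more than 28 days for Grade 4 cytopenia. If collection stops while such an event is open, its DLT status may never be settled. Under 4.1.1 a subject with no recorded DLT who misses the Day 28 assessments is replaced, and the DLT Evaluable Set likewise leaves out a subject without a DLT who misses the Day 29 assessments.

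Deaths after a subject leaves are also at issue, since this is a first-in-human gene-edited cell product. A site that applies 7.2 literally would stop collecting information that 8.5.6 requires and 7.3 permits, even where the subject has not objected.

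**Working it through.** The documents give no figure on this point, so the check is a comparison of texts.

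1. Unreachable leads to withdrawn (7.3, explicit). This merges two categories that 7.2 and 4.2 keep apart.
2. Withdrawn leads to no further trial data (7.2, explicit). The bar covers later collection only.
3. Discontinued leads to continued AE follow-up (8.5.6, explicit and unqualified).
4. Lost leads to a survival search (7.3). This is optional: the investigator may do it where it is permitted.

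Applying these rules to four kinds of subject:

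- **Reachable, but misses visits.** 7.3 requires contact and rescheduling. The subject is not withdrawn, 7.2 does not apply, and there is no conflict.
- **Refuses further data collection.** The bar in 7.2 is proper. 8.5.6 still demands follow-up on its face, so it lacks an exception. No wording change would recover data here.
- **Leaves the study without refusing further data.** 7.2 bars collection and 8.5.6 requires it. The conflict is direct, and obtainable outcomes can be lost.
- **Lost to follow-up.** 7.3 makes the subject withdrawn, so 7.2 applies. The survival search survives as a specific permission, but AE outcomes that might be found in medical records have no such permission, while 8.5.6 still calls for them.

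The damage is therefore confined to the last two groups.

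Downstream, several SAP outputs depend on how such a subject is handled:

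- Section 6.4.2.1 reports the main reason for discontinuation, and computes follow-up from the last date known alive.
- Section 6.5.2 lists deaths from the eCRF.
- Section 5.6.2 imputes a wholly missing stop date, for an AE not marked ongoing and with a complete onset date, as the latest of the withdrawal or completion date, the death date and the onset date.

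The planned maximum is 2 arms × (18 + 9) = 54 subjects. SAP 7 says 2 were treated before termination. Neither document gives a dropout or loss rate, so no expected number of affected subjects can be derived.

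**The case against.** The strongest reply is that this is untidy drafting with little practical effect. Much of that reply stands, and it rules out four stronger readings that a reader might infer.

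- *AE follow-up is barred for anyone who stops attending.* It is not. Lost status needs repeated missed visits and failed contact attempts, and a reachable subject remains in the study.
- *The survival search is forbidden for the very subjects it is meant for.* The permission directly follows the sentence that deems them withdrawn and states its purpose, so it reads as an exception. Public records are arguably also not data collected from the subject. The tension over deaths is therefore weaker than the one over AEs. Because the search is optional and covers only lost subjects, vital status can still be missed.
- *The conflict flips a cohort from 0/3 with a DLT (escalate) to 1/3 (three more subjects).* That needs a subject who left before the resolution limit without refusing data, whose outcome could be obtained, whose event did not resolve and was not attributable to disease or lymphodepletion, and no DLT in the other subjects or the replacement. Hospital observation of at least 7 days (14 in the UK), and the rule to stay within 2 hours of the site until Day 14, make early departure less likely. The original event also stays in the safety data (4.1.1), and 6.2.1.1 has all data reviewed before escalation. The sequence is possible, but the documents do not make it the expected result.
- *The SAP would report lost subjects as withdrawn, which with 2 treated subjects could misstate half of them.* SAP 6.4.2.1 defines no reason categories, and nothing shows that either treated subject was lost.

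The reply does not remove the clash between 7.2 and 8.5.6 for a withdrawn subject with an open AE. No sentence in either section yields to the other.

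**Conclusion.** The contradiction is real, and it is minor for this study. Sections 7.2, 7.3 and 8.5.6 cannot all be followed for a subject who leaves or is lost with an open AE and has not refused further data. For that subject, the AE outcome, and with it the DLT status where resolution time decides, could go uncollected. The same holds for vital status, to a lesser degree.

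The loss cannot be sized without a dropout rate. The effect in the terminated study is probably small: 2 subjects were treated, the overall survival analysis was dropped, and deaths and individual AE data are presented in listings. In the full design of up to 54 subjects it would have mattered more.

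The conclusion assumes that sites apply 7.2 as written. It also assumes that the consent form, which was not available for this review, does not already separate leaving the study from refusing data collection.

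**What to change.** Reconcile the three protocol sections and align the SAP.

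- **7.2:** limit the closing sentence to what the subject has refused, that is, withdrawal of consent to further data collection. State that other subjects who leave keep follow-up of open AEs and vital status, from records where permitted.
- **7.3:** delete the clause that deems an unreachable subject withdrawn, and keep lost to follow-up as its own category, as 7.2 and 4.2 already do.
- **8.5.6:** add an exception for subjects who withdraw consent to data collection.
- **SAP 6.4.2.1:** use the same categories for the reasons for discontinuation.

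The cost is a few sentences. The sponsor should check whether the consent form already separates the two kinds of withdrawal; if not, one line there would do it. For the terminated study, it is enough to confirm how the disposition of the 2 treated subjects is coded before the listings are final, and to carry the wording into any successor protocol.

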7.3 Lost to Follow-up

A subject will be considered lost to follow-up if he or she repeatedly fails to return for scheduled visits and is unable to be contacted by the study site.

The following actions must be taken if a subject fails to return to the clinic for a required study visit:

- The site must attempt to contact the subject and reschedule the missed visit as soon as possible and counsel the subject on the importance of maintaining the assigned visit schedule and ascertain whether or not the subject wishes to and/or should continue in the study.
- Before a subject is deemed lost to follow up, the investigator or designee must make every effort to regain contact with the subject (where possible, 3 telephone calls and, if necessary, a

certified letter to the subject's last known mailing address or local equivalent methods). These contact attempts should be documented in the subject's medical record.

- Should the subject continue to be unreachable, he/she will be considered to have withdrawn from the study. For subjects who are lost to follow-up, the investigator can search publicly available records where permitted to ascertain survival status. This ensures that the data set(s) produced as an outcome of the study is/are as comprehensive as possible.

Discontinuation of specific sites or of the study as a whole are handled in Section [11.1.11](#).

8 STUDY ASSESSMENTS AND PROCEDURES

- Study procedures and their timing are summarized in the SoA (Section 1.3). Immediate safety concerns should be discussed with the Sponsor upon occurrence or awareness to determine if the subject should continue or discontinue study intervention.
- Adherence to the study design requirements, including those specified in the SoA, is essential and required for study conduct.

8.1 General Study Periods

8.1.1 Screening and Enrollment

Screening

The screening period will be up to 28 days, and a subject that meets all inclusion and none of the exclusion criteria will be enrolled and proceed to the leukapheresis phase in Arm 1 for subjects with AML blasts <5% of bone marrow or in Arm 2 for subjects with AML blasts \geq 5% of bone marrow.

All screening evaluations must be completed and reviewed to confirm that potential subjects meet all eligibility criteria. The investigator will maintain a screening log to record details of all subjects screened and to confirm eligibility or record reasons for screening failure, as applicable. Procedures conducted as part of the subject's routine clinical management (e.g., blood count) and obtained before signing of the informed consent form (ICF) may be utilized for screening or baseline purposes, provided the procedures met the protocol-specified criteria and were performed within the time frame defined in the SoA.

As outlined below, retesting during screening and rescreening is permitted.

Retesting During Screening

Retesting is defined as repeating laboratory tests within the same screening period.

If retesting goes beyond the 28-day screening period, the subject will be classified as a screen failure and will need to go through the rescreening process.

Rescreening

Subjects who fail to qualify for the study based on laboratory tests may be considered for rescreening at the discretion of the investigator if it is considered that the subject's status has changed, and the subject may now qualify for the study. Screening is limited to 2 attempts (initial screening and 1 additional rescreening attempt). A new informed consent is required to be signed prior to rescreening. See Section 11.1.3 for Informed Consent Process details.

Enrollment

The study population will be enrolled in 2 independent Arms.

Subjects in Arm 1 will have < 5.0% AML blasts in bone marrow on locally assessed morphology, and no evidence of blasts in peripheral blood or extramedullary disease (i.e., are in CR/CRi), and MRD identified at a frequency > 0.1% by the central laboratory, [REDACTED]

Subjects in Arm 2 will have $\geq 5.0\%$ AML blasts in BM by locally assessed morphology.

